7.2.2. ALSFRS-R

The ALSFRS-R is a quickly administered (5 min) ordinal rating scale (ratings 0-4) used to determine subjects' assessment of their capability and independence in 12 functional activities. All 12 activities are relevant in ALS. Initial validity was established by documenting that in ALS patients, change in ALSFRS-R scores correlated with change in strength over time, was closely associated with quality of life measures, and predicted survival. The test-retest reliability is greater than 0.88 for all test items. The advantages of the ALSFRS-R are that the categories are relevant to ALS, it is a sensitive and reliable tool for assessing activities of daily living function in those with ALS, and it is quickly administered. With appropriate training the ALSFRS-R can be administered with high inter-rater reliability and test-retest reliability. The ALSFRS-R can be administered by phone, again with good inter-rater and test-retest reliability. The equivalency of phone versus in-person testing, and the equivalency of study subject versus caregiver responses have also recently been established. Therefore, if necessary, the ALSFRS-R may be given to the study subject over the phone. The ALSFRS-R will be administered at the Screening, Pre-Dose Baseline, Weeks 4 and 8 Visits, or the Final Safety Visit, if applicable. All ALSFRS-R evaluators must be NEALS certified.

7.2.3. Slow Vital Capacity (Pulmonary Function Testing/Spirometry)

The vital capacity (VC) (percent of predicted normal) will be determined, using the slow VC (SVC) method with normalization to percent predicted based on age, height, and gender. The SVC can be measured using conventional spirometers that have had a calibration check prior to subject testing. A printout from the spirometer of all SVC trials will be retained. All SVC evaluators must be NEALS certified. Three SVC trials are required for each testing session, however up to 5 trials may be performed if the variability between the highest and second highest SVC is 10% or greater for the first 3 trials. Only the 3 best trials are recorded on the CRF. The highest SVC recorded is utilized for eligibility. The SVC will be completed at the Screening, Pre-Dose Baseline, Weeks 4 and 8 Visits, or the Final Safety Visit, if applicable.

7.2.4. Hand Held Dynamometry (HHD)

The abductor pollicis brevis (APB) muscle will be measured by hand held dynamometry (HHD). The APB will be tested at the Screening, Pre-Dose Baseline, Weeks 4, and 8 Visits, or the Final Safety Visit, if applicable. The APB testing via HHD must always be completed prior to TMS.

7.2.5. Edinburgh Handedness Inventory Short Form

The Edinburgh Handedness Inventory Short Form is a common instrument used to assess handedness and is important in interpreting the neurophysiological data. This will be completed at the Screening Visit.

7.2.6. Blindedness Questionnaire and Exit Survey

The Blindedness Questionnaire will be used to determine whether there is effective unblinding due to treatment effects, as assessed by the subject and a member of the study team. The Exit Survey will assess subject tolerance of components of the study, including TMS and TTNCS. The exit survey will be completed at the Week 8 Visit or the Final Safety Visit, if applicable.

7.2.7. RAND-36

The RAND 36-Item Health Survey taps eight health concepts: physical functioning, bodily pain, role limitations due to physical health problems, role limitations due to personal or emotional problems, emotional well-being, social functioning, energy/fatigue, and general health perceptions. It also includes a single item that provides an indication of perceived change in health.

Scoring the RAND 36-Item Health Survey is a two-step process. First, numeric values are recoded so that a high score defines a more favorable health state and then scaled to a 0 to 100 range so that the lowest and highest possible scores are 0 and 100, respectively. Scores represent the percentage of total possible score achieved. Second, items in the same scale are averaged together to create 8 scale scores. Hence, scale scores represent the average for all items in the scale that the respondent answered.

7.2.8. Assessment of Muscle Cramps and Fasciculations

The effects of mexiletine on muscle cramps will also be assessed as a secondary endpoint. Cramps in SALS patients are common and are often debilitating. Various medications including quinine sulfate, magnesium, lioresal, dantrolene, clonazepam, diphenylhydantoin and gabapentin, have been used in the treatment of cramps in ALS, though few have been studied in the ALS population and none have clearly shown efficacy. Mexiletine has been shown to have a beneficial impact on muscle cramps in a small non-randomized study of patients with Machado-Joseph disease [45] but has never been studied in ALS patients until the recent safety and tolerable study using mexiletine.

The visual analog scale (VAS) is a scale that measures pain associated with muscle cramping. It will be used to measure muscle cramping in this study. The scale rating is from 0-10; 0 equals no symptoms, 10 equals most severe symptoms. The VAS will be explained at the Baseline visit to all subjects. It will then be completed each day by the subject and entered on a muscle cramps and fasciculations diary. At baseline, subjects will be asked to recount the number and intensity on VAS of muscle cramps experienced in the previous 7 and 30 days. At each visit (beginning at the Week 4 Visit), the coordinator will review the Muscle Cramp/Fasciculations Diary and complete a Muscle Cramp CRF based on this data and/or subject's verbal self-report. Cramp intensity as assessed by a VAS is the most common measure used in cramp trials [44].

Fasciculations will also be recorded in the diary on a daily basis, graded in the following manner: 0. no fasciculations on this day; 1. fasciculations after exertion only, not substantially interfering with daily activity; 2. fasciculations at rest or after exertion, not substantially interfering with daily activity; and 3. fasciculations at rest or after exertion and substantially interfering with daily activity. At baseline, subjects will be asked several questions related to their fasciculations experienced in the previous 14 days. Subjects will be provided with a muscle cramps and fasciculations diary to record muscle cramp frequency and intensity and severity of

fasciculations at home daily. At each subsequent visit, the coordinators will review the diary and record the daily frequency and maximal intensity of muscle cramps and fasciculations before returning the diary or providing the subject with a new diary.

7.2.9. Training and Validation

All Evaluators must be NEALS certified for ALSFRS-R and SVC; specific certification requirements are outlined in the study manual of operations. Repeat NEALS certification will be required on bi-annual basis for all outcome measures. It is strongly preferred that a single Evaluator performs all measures throughout the study. NEALS certification is required for all Evaluators prior to performing any study tests. Additionally, Evaluators will receive separate certification following a TMS and TTNCS training session immediately after the site investigator meeting.

8.0. STUDY PROCEDURES

No study procedures or obtainment of biospecimens will be performed prior to the signing of the informed consent form. All subjects will sign an informed consent form prior to undergoing any study tests or procedures. The order of testing will be at the discretion of each Site Investigator with the exception of APB testing via HHD. That must always be completed prior to TMS.

It is strongly encouraged that each visit and the procedures be completed on the same day. However, if this is not possible visits can be split up into 2 consecutive days. For the baseline visit, all measurements and procedures must be completed prior to initiating treatment. For the week 4 visits, all measurements and procedures must be completed after study drug is finished. Visit windows are consecutive calendar days and the target visit dates are calculated from the day study drug is started (i.e. the day of the Baseline Visit – Post-Dose). Study visits have the following visit windows:

Table 7. Visit Windows

	Baseline Visit (Pre-Dose)	Baseline Visit (Post-Dose)	Week 1 Safety Telephone Visit	Week 4 Visit	Week 8 Visit
Visit Window	Within 21 days of Screening Visit	1-2 hours after administration of study drug	7 ± 3 days from Baseline	29 + 3 days from Baseline	56 ± 3 days from Baseline

Subjects who withdraw consent will be asked to come in for a Final Safety Visit.

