2.2.1. Pharmacokinetics

2.2.1.1. Absorption, Distribution, Elimination and Metabolism

Mexiletine is well absorbed (~90%) from the gastrointestinal tract. Unlike lidocaine, its first-pass metabolism is low. Peak blood levels are reached in two to three hours. In normal subjects, the plasma elimination half-life of mexiletine is approximately 10 to 12 hours. It is 50 to 60% bound to plasma protein, with a volume of distribution of 5 to 7 liters/kg. Mexiletine is mainly metabolized in the liver, the primary pathway being CYP2D6 metabolism, although it is also a substrate for CYP1A2. With involvement of CYP2D6, there can be either poor or extensive metabolizer phenotypes. Since approximately 90% of mexiletine hydrochloride is metabolized in the liver into inactive metabolites, pathological changes in the liver can restrict hepatic clearance of mexiletine hydrochloride and its metabolites. The metabolic degradation proceeds via various pathways including aromatic and aliphatic hydroxylation, dealkylation, deamination and N-oxidation. Several of the resulting metabolites are submitted to further conjugation with glucuronic acid (phase II metabolism); among these are the major metabolites p-hydroxymexiletine, hydroxy-methylmexiletine and N-hydroxy-mexiletine. Approximately 10%

is excreted unchanged by the kidney. While urinary pH does not normally have much influence on elimination, marked changes in urinary pH influence the rate of excretion: acidification accelerates excretion, while alkalinization retards it.

Several metabolites of mexiletine have shown minimal antiarrhythmics activity in animal models. The most active is the minor metabolite N-methylmexiletine, which is less than 20% as potent as mexiletine. The urinary excretion of N-methylmexiletine in man is less than 0.5%. Thus the therapeutic activity of mexiletine is due to the parent compound.

Hepatic impairment prolongs the elimination half-life of mexiletine. In eight patients with moderate to severe liver disease, the mean half-life was approximately 25 hours.

Consistent with the limited renal elimination of mexiletine, little change in the half-life has been detected in patients with reduced renal function. In eight patients with creatinine clearance less than 10 mL/min, the mean plasma elimination half-life was 15.7 hours; in seven patients with creatinine clearance between 11 to 40 mL/min, the mean half-life was 13.4 hours.

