Secondary outcome measures will include effects on MEP amplitude % and CSP measured by single pulse TMS, and SICI by dual pulse TMS, as additional pharmacodynamics markers of cortical hyperexcitability and TTNCs as a pharmacodynamic marker of peripheral motor axonal hyperexcitability (and therefore a potential marker for the therapeutic effect of mexiletine on muscle cramps and fasciculations), prior to and following treatment with mexiletine or placebo and then again after withdrawal of treatment. Safety and tolerability and determination of mexiletine concentrations in blood at the time of each of the two post-baseline TMS studies will also be assessed. Additionally, the effects on muscle cramps and fasciculations will be determined utilizing an Assessment Form at Baseline, and by employing a daily muscle cramping and fasciculations diary describing both frequency and severity of these symptoms from the Baseline Visit through the Week 8 Visit. Finally, ALSFRS-R, APB testing via HHD, and SVC will be obtained at Screening, Pre-Dose Baseline, Week 4, and Week 8 or the Final Safety Visit, if applicable.

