6.2.1. Dosage Initiation/Escalation

Given the gastrointestinal (GI) side effects to taking mexiletine, a titration approach was chosen for this study. Mexiletine will be supplied as 150 mg capsules in bottles containing 60 capsules. Study drug kits will contain two bottles labeled 1 and 2. Each participant will start with 1 capsule a day, the first dose taken at the Baseline Visit and the second taken in the am from bottle 1 for 2 days (Day 1 – 2). Subjects will follow the titration schedule illustrated below in Table 5 until the full study dosage level is reached at Day 7. After initial titration, subjects will take 2 capsules of study drug in the morning and in the evening. One capsule will be taken from each bottle labeled with a 1 in the morning and evening until the Week 4 Visit. Each bottle is good for 4 weeks of dosing.

Table 5. Study Drug Titration Schedule

Number of capsules per bottle per day – Bottle 1 and 2

	Day 1-2	Day 3-4	Day 5-6	Day 7
Bottle #1	1 QD	1 BID	1 BID	1 BID
Bottle #2	-	-	1 Q AM	1 BID

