8.1.5. Week 4 Visit

This visit will take place $29 + 3$ days after the Baseline Visit. **Please note this visit must occur on Day 29, Day 30, Day 31, or Day 32. The visit cannot occur before Day 29. Study drug is to be taken for at least 28 days. The last dose will be the night before the scheduled visit.**

The following procedures will be performed:

- Perform physical and neurological examinations
- Measure vital signs and weight
- Perform 12-lead ECG
- Collect blood samples for clinical laboratory assessments including:
 - Hematology and differential panel
 - Blood chemistry panel
 - Urine pregnancy test (for woman of childbearing potential [WOCBP])
- Collect blood for plasma mexiletine level and plasma for NEALS biorepository
- Administer ALSFRS-R questionnaire
- Administer RAND-36
- Perform APB testing by HHD
- Perform SVC
- Perform TMS/TTNCS
- Review and document concomitant medications and therapies
- Assess and document AEs
- Check study drug compliance and dosing diary
- Collect Muscle Cramp/Fasciculations Diary and dispense new Diary to subject
- Perform study drug accountability and collect all unused study drug and empty containers
- Schedule the Week 8 Visit

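### A split Week 4 visit may put TMS about 36 hours, not about 12 hours, after the last dose, at 19–25% of the planned trough level, and separate it from its plasma sample

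*Protocol*

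**What the plan says.** Protocol 8.0 strongly encourages completing each visit in one day, then adds: "However, if this is not possible visits can be split up into 2 consecutive days". On sequence it says: "The order of testing will be at the discretion of each Site Investigator with the exception of APB testing via HHD", and dynamometry must come before TMS. It also states: "For the week 4 visits, all measurements and procedures must be completed after study drug is finished".

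Protocol 8.1.5 fixes the end of dosing: "The last dose will be the night before the scheduled visit". At target dose the regimen is twice daily (Protocol 6.2.1: "subjects will take 2 capsules of study drug in the morning and in the evening"), so a test the next morning is at trough, about 12 hours after the last dose. Footnote 6 to the schedule of events, in both the Protocol and the SAP, describes the blood draw as a trough level. Protocol 4.1 ties that level to the electrophysiology by calling for "determination of mexiletine concentrations in blood at the time of each of the two post-baseline TMS studies".

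On pharmacokinetics, Protocol 2.2.1.1 says that in normal subjects "the plasma elimination half-life of mexiletine is approximately 10 to 12 hours", and "Peak blood levels are reached in two to three hours".

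SAP 3.7.1 makes the primary comparison the change in RMT to Week 4, both active arms pooled against placebo, two-sided alpha 0.05. The separate dose comparisons at alpha 0.027 are secondary (SAP 3.7.2 and 3.7.6).

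**The concern.** Taken together, these rules allow the primary measurement on the second day of a split Week 4 visit with no dose in between. Nothing requires TMS or the plasma sample on the first day, and nothing caps the time from last dose to TMS. Protocol 7.2.1 asks only for a consistent morning or afternoon slot, which a day-two morning test satisfies.

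Such a record is coded as Week 4 like any other, although it was taken one day into washout. If the RMT effect depends on current drug level, these records pull the treatment difference toward zero in a trial of about 60 people built to detect a pharmacodynamic signal. A plasma sample drawn on the other day would also misstate exposure at the time of TMS.

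The analysis plan does not compensate. The SAP model has terms for visit, treatment by post-baseline visit, and random intercepts and slopes, but none for time since last dose. The TMS quality flags (SAP 3.3.1) do not consider it. Protocol 13.6 plans an analysis by serum level, but SAP 3.7.2 does not list it, and the SAP's introduction gives the SAP authority on analysis.

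**Working it through.** **Inputs.** Half-life 10–12 h in normal subjects (Protocol 2.2.1.1). Last dose the evening before the visit (8.1.5). SD of 4-week RMT change 5.1%, detectable effect 5.3%, 60 randomised 1:1:1, 10% loss (18 per arm), per-dose two-sided alpha 0.027 (Protocol 13.9, SAP 3.4). Pooled test at alpha 0.05 (SAP 3.7.1).

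**Step 1: reproduce the stated power.** Standard error per dose = 5.1 × √(1/18 + 1/18) = 1.70. Noncentrality = 5.3 / 1.70 = 3.12. With 51 error degrees of freedom the critical t is 2.28 and power is 79.7%, matching the stated 80%.

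The plan gives no power for the pooled test. If both doses carry the same 5.3% effect (assumption), standard error = 5.1 × √(1/18 + 1/36) = 1.47, noncentrality = 3.60, critical t = 2.01, power about 94%.

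**Step 2: drug level at TMS.** Fraction of the level at last dose remaining after t hours = 0.5^(t / half-life).
- At 12 h: 0.5^(12/10) = 0.44; 0.5^(12/12) = 0.50.
- At 36 h: 0.5^(36/10) = 0.08; 0.5^(36/12) = 0.125.
- Day two relative to the planned test: 0.5^(24/10) = 0.19; 0.5^(24/12) = 0.25.

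A one-compartment steady-state model with twice-daily dosing and a peak at 2–3 h gives the same ratio, 0.19–0.25.

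**Step 3: dilution.** Let f be the share of Week 4 TMS done on day two and r the ratio from Step 2. If effect is proportional to plasma level, mean effect = 5.3 × [1 − f(1 − r)]. For f = 20%: 5.3 × (1 − 0.2 × 0.81) = 4.4 and 5.3 × (1 − 0.2 × 0.75) = 4.5.

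**Step 4: power at the diluted effect.** Standard errors and critical values as in Step 1. The documents give no value for f, so a range is shown.

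| f | Mean effect (%) | Pooled primary test, alpha 0.05 | Per-dose secondary test, alpha 0.027 |
|---|---|---|---|
| 0 | 5.3 | about 94% | about 80% |
| 5% | 5.1 | 92% | 76% |
| 10% | 4.9 | 90% | 72–73% |
| 20% | 4.4–4.5 | 84–85% | 63–65% |

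These figures use the plan's own simple ANOVA approximation, which it calls conservative relative to the mixed model.

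**The case against.** The strongest objection concerns size. Same-day completion is strongly encouraged and splitting is a fallback, so f may be very small. A share of 20% would need 40% of participants to split the visit if TMS were equally likely to fall on either day (0.20 / 0.5). Across the tabulated shares the primary pooled test stays above 80% power. A reader might quote the fall from 80% to 63–65% as the loss for the primary analysis. It is not: that figure belongs to the per-dose tests, which the SAP makes secondary.

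A reader might also infer that the effect is essentially gone by day two. The documents do not show this. They give no relation between concentration and RMT, and Protocol 13.6 allows for a sustained benefit at 8 weeks. The half-life is for normal subjects; with the 25 h that Protocol 2.2.1.1 reports in liver disease, the day-two ratio would be 0.5^(24/25) = 0.51. Nor is it fair to set the roughly one-tenth remaining at 36 h against a full level, because the planned test is itself at trough, with 44–50% remaining.

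The mITT sample (SAP 3.5) already keeps observations made after permanent discontinuation, so Week 4 RMT is not strictly an on-drug value. That holds, but a scheduling delay in someone who took the full course is a measurement artefact, not part of the treatment policy being estimated. Under blinding, splitting should not differ by arm; it can attenuate an effect but gives no reason to expect a false one.

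Finally, the wording on a trough level and on sampling at the time of TMS can be read as already tying the two together. It states the intent, but Protocol 8.0 supplies no rule that enforces it, and Protocol 7.1.3 calls the sample both random and trough.

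**Conclusion.** The gap is real: a site can comply fully and still measure the primary endpoint about 36 h after the last dose, at 19–25% of the planned trough level, with the plasma sample on a different day. Any resulting bias is toward no effect.

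Its size is uncertain. It rests on two assumptions that the documents neither support nor contradict: that the RMT effect follows plasma level, and the share of day-two tests. Over shares of 5–20% the cost to the primary test is about 2 to 10 percentage points of power, from about 94%. The secondary per-dose tests lose about 4 to 17 points, from about 80%. The documents do not support a claim that the primary test becomes underpowered, or that dilution will occur to any particular degree. This is a cheap improvement worth making, not a flaw that invalidates the design.

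**What to change.** In Protocol 8.0 and 8.1.5, state that if the Week 4 visit is split, hand-held dynamometry, TMS, TTNCS and the plasma mexiletine sample are all done on the first day. Dynamometry is included because it must precede TMS. Other procedures remain free to move to the second day. Dosing is unchanged.

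Record on the CRF the clock times of the last dose, TMS and the plasma draw, so that departures can be seen.

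A supportive sensitivity analysis by time since last dose could be added to SAP 3.7.2. It is optional: with about 18 evaluable participants per arm and probably few day-two tests it would carry limited information, and excluding records on a post-randomisation scheduling variable has its own drawbacks.

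The cost is a sentence in each of two sections, three CRF time fields and slightly less scheduling freedom for sites.

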8.1. Schedule of Study Procedures

8.1.1. Screening Visit

The following procedures will be performed at the Screening Visit:

- Obtain written informed consent from subject
- Assess inclusion and exclusion criteria
- Obtain medical history and demographics
- Obtain ALS diagnosis and ALS history
- Perform physical and neurological examinations
- Measure vital signs including height & weight
- Perform APB testing by HHD
- Perform 12-lead ECG
- Collect blood samples for clinical laboratory assessments including:
 - Hematology and differential panel
 - Blood chemistry panel
 - Serum pregnancy test (for woman of childbearing potential [WOCBP])
- Perform TMS and NCS to determine if subject meets inclusion criteria

- Administer ALSFRS-R questionnaire
- Edinburgh Handedness Inventory Short Form
- Perform slow vital capacity (SVC)
- Review and document concomitant medications and therapies
- Assess and document AEs after subject signs informed consent form
- Schedule the Baseline Visit within 21 days

8.1.2. Pre-dose Baseline Visit

This visit will take place within 21 days of the Screening Visit. The following procedures will be performed:

- Assess inclusion and exclusion criteria (Note: Baseline Visit SVC is not exclusionary, even if below 50%)
- Measure vital signs and weight
- Administer ALSFRS-R questionnaire
- Perform APB testing by HHD
- Perform SVC
- Administer RAND-36
- Muscle Cramps/Fasciculations Assessment
- Perform TMS/TTNCS
- Review and document concomitant medications and therapies
- Collect blood for plasma mexiletine level, DNA and plasma for NEALS biorepository
- Urine pregnancy test (for woman of childbearing potential [WOCBP])
- Assess and document AEs
- Distribute Muscle Cramps/Fasciculations Diary
- Randomize subject*
- Administer first dose of the study drug on site. The subject will be observed at the site for 60-120 minutes by an appropriate healthcare staff member according to the site's institutional/state regulations to assess any immediate reaction to the study drug.

**Randomization should occur as close to the Baseline Visit as possible to give enough time for the site pharmacy to distribute the study drug kits (usually 24-48 hours in advance of the Baseline Visit).*

